4.6 Restenting

Restenting with a non-study stent will take place if there is no improvement of clinical status (see definition in secondary endpoint 2) and associated persistence of the stricture based on imaging. Imaging will be conducted per standard of practice. Such may be prompted by lack of improved clinical status and may consist of non-invasive imaging or of a pancreatogram. A pancreatogram will only be performed if an ERCP is necessitated for a reintervention with or without restenting.

Restenting with a new study stent may only occur during the initial stent placement procedure for conditions such as stent misplacement, improper stent size choice, and other conditions, as necessary.

August 28, 2017

Boston Scientific
WallFlex Pancreatic Pivotal Protocol
91067616 Rev/Ver AK
Page 22 of 64

5 Patient Selection

5.1 Inclusion Criteria

Patients who meet all of the following criteria may be given consideration for inclusion in this clinical investigation, provided no exclusion criterion is met.

1. Age 18 or older
2. Willing and able to comply with study procedures and follow-up schedule and provide written informed consent to participate in study
3. Chronic pancreatitis induced stricture of Cremer Type IV, namely distal dominant stricture with upstream ductal dilation.
4. For patients with a prior plastic pancreatic stent: VAS Pain Score and Frequency of Pain sectors of the Izbicki pain scale at the time of placement of the plastic stent.
5. Availability of narcotic dosage for at least one month prior to baseline visit for patients who do not have a prior plastic pancreatic stent or availability for one month prior to placement of prior plastic pancreatic stent, where applicable.
6. VAS Pain Score of ≥ 20 before study stent placement for patients without a prior plastic pancreatic stent. VAS Pain Score of ≥ 20 before initial plastic pancreatic stent placement for patients with a prior plastic pancreatic stent indwelling for 90 days or less before study stent placement. VAS Pain Score is captured via Izbicki pain scale.
7. Pain occurring weekly or more frequently (assessed by Frequency of Pain sector of the Izbicki pain scale) as reported before study stent placement for patients without a prior plastic pancreatic stent, or before placement of initial plastic pancreatic stent for patients with a prior plastic pancreatic stent indwelling for 90 days or less before study stent placement.
8. Minimum 5 mm diameter of dilated duct immediately upstream of pancreatic duct stricture
9. Prior clearance of pancreatic stones where needed
 - If pancreatic duct stone clearance prior to placement of the study stent includes ESWL, then a plastic pancreatic stent may be placed immediately after the ESWL procedure at the discretion of the Investigator, for example, if there is concern about stone fragments or stone sludge in side branches of the pancreatic duct, and may be left indwelling for 30-90 days.
 - If new pancreatic duct stones requiring ESWL have formed by the time of intended study stent placement, then the patient will not receive the study stent and be excluded from the study. Further treatment of the patient will be provided per standard of practice outside of the study. In case the study stent is not placed during the same session in which the plastic stent is removed, the pain score needs to be collected again prior to study stent placement.
10. Prior endoscopic pancreatic sphincterotomy (EPS), historically or to be provided at time of SEMS placement as applicable

August 28, 2017

Boston Scientific
 WallFlex Pancreatic Pivotal Protocol
 91067616 Rev/Ver AK
 Page 23 of 64

5.2 Exclusion Criteria

Patients who meet any one of the following criteria will be excluded from this clinical study.

1. Pancreatic or peri-ampullary cancer with or without pancreatic duct strictures caused by malignancy
2. Biliary strictures caused by chronic pancreatitis that are symptomatic and/or in need of therapeutic intervention
3. Perforated duct
4. Ansa pancreatica
5. Presence of pancreatic cysts suspected to be cystic tumor or requiring transmural drainage
6. Duodenal/groove pancreatitis
7. Autoimmune pancreatitis
8. Pancreatic duct stenoses not located in the head of the pancreas
9. Failed access during an attempted ERCP on a prior date at the investigational center
10. Duration of indwell of one single plastic pancreatic stent or cumulative duration of consecutive single plastic pancreatic stents immediately prior to study stent placement exceeding 90 days
11. History of prior single pancreatic plastic stent(s) followed by a stent-free period shorter than 1 year before enrollment into the study
12. History of prior side-by-side multiple pancreatic plastic stents up to one year prior to enrollment
13. History of prior pancreatic metal stent(s)
14. Reported recent history of acute relapsing pancreatitis in the absence of chronic pancreatitis
15. Patients for whom endoscopic techniques are contraindicated.
16. Patients who are currently enrolled in another investigational study that would directly interfere with the current study, without prior written approval from the sponsor
17. Inability or refusal to comply with the follow-up schedule including patient living at such a distance from the investigational center that attending follow-up visits would be unusually difficult or burdensome

August 28, 2017

Boston Scientific
WallFlex Pancreatic Pivotal Protocol
91067616 Rev/Ver AK
Page 24 of 64

6 Patient Accountability

6.1 Patient Status and Classification

6.1.1 Enrolled Cohort

A patient is considered “enrolled” after signing the study-specific Informed Consent Form (ICF). Patients who sign the ICF but subsequently do not meet one or more of the selection criteria will be considered screen failures and excluded from the study.

6.1.2 Intent-to-Treat Cohort

This cohort (ITT) consists of those “enrolled” patients who meet all inclusion/exclusion criteria. Any adverse events occurring or resulting from a treatment attempt will be collected. Protocol deviations will be collected as necessary. Patients in this cohort will be counted towards the enrollment ceiling, and this cohort will be considered the primary analysis cohort.

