7.3 Informed Consent

Written Informed Consent must be obtained for all patients who are potential study candidates. Patients will be asked to sign the Informed Consent form before any study-specific tests or procedures are performed. The Informed Consent form is study-specific and must be approved by the study Institutional Review Board (IRB)/Ethics Committee (EC) and Competent Authority, as applicable. Study personnel should explain that even if a patient agrees to participate in the study and signs the ICF, the ERCP procedure may demonstrate that the patient is not a suitable candidate for the study.

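### Eligibility has no cut-off date in the cohort definitions, so a patient with a study stent placed or attempted who is later found ineligible falls outside both primary analyses

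*Combined protocol and SAP*

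**What the plan says.** Under section 6.1.1 a patient is enrolled on signing the consent form, before any study procedure. Patients who then "subsequently do not meet one or more of the selection criteria will be considered screen failures and excluded from the study". Section 6.1.2 defines ITT as enrolled "patients who meet all inclusion/exclusion criteria" and adds that "this cohort will be considered the primary analysis cohort". Section 6.1.3 defines per-protocol as the ITT patients who receive a study stent and have no major protocol deviation.

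Some eligibility findings come after consent. Section 7.3 warns that "the ERCP procedure may demonstrate that the patient is not a suitable candidate for the study". Under inclusion criterion 9 (section 5.1), if new stones needing lithotripsy are present when the study stent is due, "then the patient will not receive the study stent and be excluded from the study". Other criteria, such as cancer or the duration of prior plastic stenting, could be found not to be met only after the stent is in.

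One group is explicitly protected. Section 8.1.1 keeps plastic-stent patients who are below the pain thresholds at stent exchange in the safety analysis, although they leave the effectiveness analysis. Section 7.12 says that patients who receive the study stent are followed until 6 months after removal or observed complete distal migration, with no exception for ineligibility. The safety endpoint (sections 4.2 and 8.1.1) counts related serious adverse events (SAEs) from stent placement onward.

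**The concern.** The two cohort sentences together work as a removal rule with no end date. Take a patient stented in good faith whose plastic-stent indwell is later found to have exceeded 90 days, or whose stricture later proves malignant. That patient does not meet all criteria, so by 6.1.1 is a screen failure and by 6.1.2 is not in ITT. The usual place for such a patient is inside ITT as a protocol deviation, removed only from per-protocol. Here the removal happens one level higher.

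This matters because each primary endpoint is a single-arm exact test against a fixed goal, with a small margin in patient counts. Membership of the primary cohort should not depend on information that arrives after treatment. The planned sensitivity analyses do not help: counting missing data as failures and the tipping-point analysis (sections 8.1.2 and 8.1.3) act on patients inside the cohort, and a reclassified patient is outside it.

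**Working it through.** **Inputs.** Safety goal 32%, assumed rate 15%; effectiveness goal 53%, assumed rate 75% (section 8.1.2). Exact test, one-sided alpha 0.025, power 80% (synopsis). 64 ITT patients after a 10% allowance, and up to 92 enrolled (section 8.1.2). The number of reclassified patients, m, is not in the documents and is assumed.

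**The plan's own figures.**
- Safety: the largest k with P(X ≤ k | n, 0.32) ≤ 0.025. At n=57, k=11, alpha 0.0242, power 0.862. At n=56 power is 0.789. So 57 reproduces.
- Effectiveness: the smallest r with P(X ≥ r | n, 0.53) ≤ 0.025. At n=43, r=30, alpha 0.0190, power 0.834. At n=42 power is 0.766. So 43 reproduces.
- 57/0.9 = 63.3, rounded up to 64. 64/0.7 = 91.4, rounded up to 92.

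The sample size is sound. The issue is who is counted.

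**Safety at n=92.** The limits are 20 events at n=92, 20 at n=91 and 19 at n=90.
- Full cohort, 21/92: P(X ≤ 21 | 92, 0.32) = 0.035, fails.
- One event patient reclassified, 20/91: P(X ≤ 20 | 91, 0.32) = 0.024, passes.
- Two event patients reclassified, 19/90: p = 0.015, passes.

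**Worst-case type I error.** Suppose every one of the m removed patients had an event. The test then passes when X − m ≤ k(N − m), where X is the true number of events among the N patients placed or attempted. The error is the probability of that at a true rate of 32%.

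| N | m | limit after removal | true events that pass | type I error |
|---|---|---|---|---|
| 64 | 0 | 12 | 12 | 0.013 |
| 64 | 1 | 12 | 13 | 0.027 |
| 64 | 2 | 12 | 14 | 0.051 |
| 92 | 0 | 20 | 20 | 0.020 |
| 92 | 1 | 20 | 21 | 0.035 |
| 92 | 2 | 19 | 21 | 0.035 |
| 92 | 3 | 19 | 22 | 0.058 |

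**Effectiveness at n=64, true rate 53%.** The full cohort needs 43 successes (alpha 0.015). With one failure removed, 42 of 63 suffice, and the error is P(X ≥ 42 | 64, 0.53) = 0.028.

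**Removal unrelated to outcome.** Reclassification can also count against the device. 20/92 passes, but removing two event-free patients gives 20/90, which exceeds the limit of 19 and fails.

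**The case against.** The best reply is that the authors meant eligibility to be settled before stenting. The eligibility assessment is listed only at Screening/Baseline (section 7.5) and not at placement or later visits. The stated re-checks, for new stones (section 5.1) and pain thresholds (section 8.1.1), come before the study stent goes in. Section 4.4 says that patients meeting all criteria receive the stent, and no passage calls a stented patient a screen failure. That is a fair account of intent and suggests that the fix will be uncontroversial. It does not supply the missing cut-off: 6.1.1 and 6.1.2 are the operative definitions, and their wording reaches a treated patient.

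A second reply is that adverse events from a treatment attempt are collected (section 6.1.2) and related events after consent are recorded (section 16.1). Neither section says that they count in the endpoint for a patient outside ITT.

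The reply on size is also fair. Exactly 21/92 has a probability of about 1.4% at a true rate of 15% and 1.5% at 32%, and the inflated errors assume that every removed patient had an event or was a failure.

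Three stronger readings are tempting, and the documents do not support them.
- Because "Perforated duct" is an undated exclusion, a reader might infer that a perforation caused by the study ERCP makes the patient ineligible. Section 15.1 lists perforation and duct rupture as anticipated adverse effects, and the safety endpoint covers events related to the stenting procedure. The exclusion is more naturally read as a pre-existing condition.
- A reader might infer that reclassified stented patients lose follow-up. Section 7.12 says otherwise, so this is a conflict between two sections and not a stated loss.
- A reader might infer that harmed or non-responding patients are the most likely to be reclassified. Nothing in the documents shows this, and no retrospective eligibility review is described. An excess in plastic-stent indwell has no evident link to outcome.

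**Conclusion.** The point holds as a defect of definition. As written, a patient with a study stent placed or attempted who is later found ineligible is outside both primary analyses, and no clause comparable to the one in section 8.1.1 brings that patient back. Sections 6.1.1 and 7.12 also disagree on whether such a patient remains in the study once stented.

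The size cannot be estimated from the documents. In the worst case one reclassified event patient is enough to turn a failed safety test at n=92 into a pass, and at n=64 one takes type I error just past the nominal 0.025 and two about double it. These figures assume that the removed patients had events; they bound the problem and do not forecast it. The direction of any actual bias is not established. The change is worth making because it is cheap and takes treated-patient membership of the primary cohort out of later judgement.

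**What to change.** Amend sections 6.1.1, 6.1.2, 4.2 and 8.1.1 as follows.

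1. State that eligibility is fixed immediately before study stent insertion is attempted, after any diagnostic findings of that ERCP. This leaves room for section 7.3, where the ERCP itself may settle suitability.
2. Limit screen failure to patients in whom no study stent placement was attempted because a criterion was not met.
3. Define ITT as all eligible patients, as now, plus every patient in whom study stent placement was attempted. Eligible patients who are never attempted stay in.
4. Treat ineligibility found later as a protocol deviation, handled only in the per-protocol cohort.
5. Start the primary safety window at the placement attempt. Otherwise an SAE in an attempted but unstented patient may not count even though the patient is in ITT.
6. Reconcile 6.1.1 with 7.12 on the follow-up of stented patients found ineligible.

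The cost is a few sentences; 43, 57, 64 and 92 are unchanged. The downside is that a few ineligible patients stay in the primary analysis, which the per-protocol analysis already addresses.

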4.2 Primary Safety Endpoint

Primary Safety Endpoint:

Rate of related SAEs from WallFlex Pancreatic stent placement to end of study.

Relatedness will be determined by the PI, reporting if the SAE is related to the study stenting procedure, to the indwelling study stent, to study stent removal and/or to study stent migration.

Pain thought to be caused by WallFlex Pancreatic stent expansion will be reported, but will not count towards the endpoint if all three of the following conditions apply:

1. Pain can be managed by medication, with the exception of injectable narcotic use for more than 24 hours.
2. Pain does not cause WallFlex Pancreatic stent removal.
3. Pain resolves by 72 hours after WallFlex Pancreatic stent placement.

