6.1.3 Per-Protocol Cohort

The per-protocol cohort is a subset of the ITT patients who receive a study stent(s) and who do not experience major protocol deviations (ICH E9 definitions).

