For the patients who have a single plastic stent in place for up to 90 days before receiving the study stent, inclusion criteria #6 and #7 will be reassessed immediately prior to the plastic to study stent exchange. Patients who do not meet the inclusion criteria levels of the VAS pain score (≥ 20) and frequency of pain score (50, 75, or 100) at the time of stent exchange will be excluded from the primary effectiveness endpoint analyses but will be included in the primary safety endpoint analysis and all secondary endpoint analyses. For the patients who meet the inclusion criteria levels, we will use the scores (VAS Pain Score and Frequency of Pain Score) collected immediately prior to the plastic to study stent exchange as their baseline and include them in the primary effectiveness endpoint analyses.

Primary Safety Endpoint:

August 28, 2017

Boston Scientific
WallFlex Pancreatic Pivotal Protocol
91067616 Rev/Ver AK
Page 32 of 64

Rate of related Serious Adverse Events (SAEs) from WallFlex Pancreatic stent placement to end of study.

Relatedness will be determined by the PI, reporting if the SAE is related to the study stenting procedure, to the indwelling study stent, to study stent removal and/or to study stent migration.

Pain thought to be caused by WallFlex Pancreatic stent expansion will be reported, but will not count towards the endpoint if all three of the following conditions apply:⁵

1. Pain can be managed by medication, with the exception of injectable narcotic use for more than 24 hours.
2. Pain does not cause WallFlex Pancreatic stent removal.
3. Pain resolves by 72 hours after WallFlex Pancreatic stent placement.

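### As written, the primary safety test uses an ITT denominator that can include eligible patients who never reach study stent placement, although related SAEs count only from placement

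*Combined protocol and SAP*

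**What the plan says.** - **Cohorts.** Section 6.1.2 defines ITT as enrolled "patients who meet all inclusion/exclusion criteria" and adds that "this cohort will be considered the primary analysis cohort". Receipt of a study stent becomes a condition only in section 6.1.3 (the per-protocol cohort is "a subset of the ITT patients who receive a study stent(s"). No safety or as-treated cohort is defined.
- **Endpoint.** Section 4.2 defines primary safety as "Rate of related SAEs from WallFlex Pancreatic stent placement to end of study"; section 8.1.1 says the same. SAEs related to the stenting procedure are among those that count.
- **Test and size.** Section 8.1.2 tests whether the related SAE rate is below 32%, assuming 15%, with one-sided alpha 0.025 and 80% power. It requires 57 patients, raised for 10% loss to 64 Intent-to-Treat patients. The synopsis specifies an exact test.
- **Enrollment ceiling.** Up to 92 patients may be enrolled. Section 8.1.1 keeps patients below the pain threshold at stent exchange in the safety analysis, so its denominator can approach 92.
- **Exits from the study.** Under section 6.1.1, consented patients who fail a selection criterion are screen failures and leave the study. Under criterion 9 of section 5.1, if new stones requiring ESWL have formed by the intended placement, "then the patient will not receive the study stent and be excluded from the study".
- **Attempts.** Section 6.1.2 states: "Any adverse events occurring or resulting from a treatment attempt will be collected".

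**The concern.** The numerator and denominator start at different points. A patient enters the ITT denominator once consented and eligible, but can contribute an event only once the study stent is placed. An eligible patient who withdraws in between adds one to the denominator and nothing to the numerator. Criterion 9 allows a plastic stent for 30 to 90 days before the study stent, so for some patients that interval is not short. Section 6.3 does not replace withdrawals.

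For a superiority comparison, ITT is usually the cautious choice. Here the aim is to show that a harm rate lies below a fixed ceiling, so patients with no exposure can only lower the observed rate. What is at stake is the false-pass probability of one of the two primary hypotheses of a pivotal single-arm study.

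**Working it through.** **Inputs.** Goal 32%, planning rate 15%, one-sided alpha 0.025, power 80%, n = 57, ITT size 64 (section 8.1.2); exact test (synopsis); ceiling 92 (section 8.1.2). The number of unstented ITT patients, m, is not given and is varied as an assumption.

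**Step 1: the plan's own figure.** For each n, the pass mark c(n) is the largest c with P(X ≤ c | n, 0.32) ≤ 0.025, and power is P(X ≤ c(n) | n, 0.15).
- n = 57: c = 11, alpha 0.0242, power 0.862.
- n = 56: c = 10, power 0.789.
- Power is at least 0.80 for every n checked from 57 to 69, so 57 is reproduced.
- Loss allowance: 57/0.90 = 63.3, rounded up to 64. Ceiling: 64/0.70 = 91.4, rounded up to 92. Both agree with the plan.

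**Step 2: error with m unstented patients in a denominator of N.** These patients cannot have an event, so the count comes from N − m patients while the pass mark is set for N. At a true 32% in stented patients:

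error = P(X ≤ c(N) | N − m, 0.32)

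| m | N = 64, pass at ≤12 | N = 92, pass at ≤20 |
|---|---|---|
| 0 | 0.0134 | 0.0203 |
| 1 | 0.0162 | 0.0237 |
| 2 | 0.0196 | 0.0276 |
| 3 | 0.0235 | 0.0320 |
| 4 | 0.0283 | 0.0371 |
| 6 | 0.0403 | 0.0494 |
| 7 | 0.0479 | 0.0568 |

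Because the exact test is discrete, the error stays within 0.025 for up to 3 unstented of 64 but only 1 of 92. The tolerance depends on the exact N: at N = 90 (pass at ≤19), 3 unstented gives 0.0248.

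**Step 3: the same thing as a pass mark.**
- 57 stented of 64 ITT: the ITT denominator passes at 12 events (12/57 = 21.1% of stented patients, error 0.0479). A stented denominator passes at 11 (19.3%, error 0.0242). A true 32% is diluted to 0.32 × 57/64 = 28.5%.
- 89 stented of 92: passes at 20 instead of 19.
- 86 stented of 92: passes at 20 instead of 18.

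The case m = 7 of 64 places the whole 10% loss allowance before placement, which is an upper reading of that allowance.

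**Step 4: after the fix.** When every patient in the denominator can contribute an event, the error is at most 0.025 by construction. With 57: pass at ≤11, error 0.0242, power 0.862. With 83 (92 less about 10%, that is 9): pass at ≤17, error 0.0140, power 0.935.

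**The case against.** **No safety denominator is named.** Sections 4.2, 8.1.1 and 8.1.2 do not name the population for the safety test. That it is ITT follows from the general statement in section 6.1.2 and from the sample size being given in ITT patients. This stands as a caveat. Even so, ITT is the only rule the plan states, and nothing overrides it for safety.

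**Most unstented patients leave the study.** A reader might infer from criterion 9 that patients who develop new stones while waiting pad the denominator. They do not: they are excluded from the study, as are screen failures. Section 7.3 also warns that the ERCP itself may show a patient to be unsuitable, and section 7.6 allows baseline and placement on the same day. This stands, and it narrows the source mainly to eligible patients who withdraw before placement.

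**Failed attempts may already count.** A reader might infer that an SAE during a failed attempt falls outside the endpoint because the window opens at placement. The documents do not settle this. Procedure-related SAEs are in the endpoint definition, events from an attempt are collected, and section 7.6 uses study stent placement as the name of the whole visit. If the window opens with the procedure, these patients can contribute events and are not padding. The wording is ambiguous rather than plainly exclusionary.

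**The size is unknown.** This stands. At most 3 unstented of 64, or 1 of 92, would leave the error within 0.025. The inflation is computed at the null rate of 32%, whereas the plan expects 15%.

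**Sensitivity analysis.** Section 8.1.3 describes adding missing data as failures, but only as something that may be done. It does not say that a patient with no post-placement period counts as missing for safety.

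**Conclusion.** The mismatch is real and its direction is known: read as written, it favors passing. It rests on taking ITT as the safety denominator, which is the plan's only stated rule but is not repeated in the safety sections, and on some eligible patients withdrawing before placement.

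The effect is modest for a few patients. The error first exceeds 0.025 at 4 unstented of 64 (0.028) or 2 of 92 (0.028), and is close to double the nominal level at 7 of 64 (0.048) or 6 of 92 (0.049). These counts are illustrations, not forecasts.

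The tempting stronger conclusion is that the trial's SAE rate will be materially diluted. The documents do not support it, because they give no count of unstented patients, remove two obvious groups of them from the study, and leave the handling of failed attempts open. The stated sample sizes are not in question.

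**What to change.** In sections 6.1 and 8.1:

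1. Define a primary safety cohort of all patients in whom study stent placement was attempted, whether or not a stent was left in place.
2. Count related SAEs from the start of that procedure to end of study, and state that failed attempts are included.
3. Test the 32% goal in that cohort, with the pass mark set by its actual size.
4. Leave the effectiveness cohort unchanged.

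The cost is protocol and SAP wording. The safety denominator may fall by a few patients, but exact power at 15% is still 86% with 57 and 93% with 83. Counting failed attempts explicitly could add events that a narrow reading of placement would have left out.
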